Qsymia provides a potential opportunity to develop an effective treatment plan that would be an adjunct to surgical intervention in the super obese patient. Use of Qsymia in addition to a low-calorie dietary prescription pre-operatively would effectively decrease weight prior to surgical intervention, lowering surgical risk to some extent. Additionally, if continued post-operatively, Qsymia as an adjunct to the post-surgical dietary plan would potentially extend the weight loss horizon so that the probability of the typical weight loss plateau at 12-18 months is decreased. The combination of the pre-operative and post-operative weight loss associated with Qsymia use could significantly diminish the need for a second surgical procedure in super obese patients. We have designed a pilot study to examine the use of Qsymia in super obese patients to determine its potential for decreasing the need for a second weight loss surgery.

Primary Objective

The primary objective of the proposed study is to demonstrate the effectiveness of using Qsymia in the superobese (BMI ≥ 50 kg/m²) as an adjunct to surgical therapy.

Secondary Objectives

Secondary objectives of the proposed study include determining tolerability of Qsymia perioperatively, determining changes in resting metabolic rate postoperatively (3 months and 12 months post-surgery), determining the magnitude of preoperative weight loss and determining the magnitude of weight loss at 12, 18, and 24 months post-surgery.

Treatment Plan

Treatment Group

Patients with a BMI ≥ 50 kg/m² that agree to participate in the experimental group will begin their treatment plan with a medical weight loss diet that includes a low-calorie diet and Qsymia at the recommended treatment dose of 7.5/46 mg daily (following initiation of the titration dose for 2 weeks). The low-calorie diet will be individually tailored based on initial resting metabolic rate measurement and co-morbid conditions. Patients will be medically monitored with once monthly medical visits and also have once monthly visits with a dietitian to review the treatment plan. Patients will receive medical weight loss therapy for a minimum of 3 months prior to proceeding to the laparoscopic sleeve gastrectomy. If a patient opts not to proceed to sleeve gastrectomy, they will continue to receive medical therapy for weight reduction including Qsymia and followed for the duration of the study (i.e., for 2 years).

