Patients will discontinue Qsymia the week prior to the scheduled operation. The sleeve gastrectomy will be performed by one of the surgeons at the Weight Management Center ([name], [name], [name]) using standard laparoscopic technique. Post-operatively, all patients will be provided with dietary counseling and a nutrition prescription for a very low calorie, high protein diet: 500-700 calories, protein goal of 1-1.2g/kg IBW, and 60-75g carbohydrate. Qsymia will be resumed in the second post-operative week at the initial titration dose and increased to the recommended treatment dose of 7.5/46 mg daily. Patients will have standard post-operative surgical follow up at months 1, 3, 6, 9, 12, 18, and 24. During the post-operative phase, all patients will be enrolled in the bariatric support group program that meets on a monthly basis. Patients will also have at least 3 visits with a clinic dietitian to review and update dietary prescriptions. At any point during this course of follow up, a determination can be made that the primary outcome event has occurred if the patient has a weight plateau—defined as weight gain or < 3 lbs weight loss—for 3 consecutive months, remains above a BMI of 39.9 kg/m² and continues to have associated co-morbidities. These patients will be evaluated for the possibility of moving forward to the next operative stage (laparoscopic Roux-en-Y gastric bypass) while all other patients will continue on with medication and diet/exercise therapy.

Control Group

Control subjects for the proposed study will be identified from the patient population at the Wake Forest Baptist Health Weight Management Center. They will be matched to subjects in the treatment group on age, sex, ethnicity, and BMI. They will be a historical control group who had surgery prior to the commencement of the proposed study (retrospective review).

Trial Design

Prospective independent historical case control

Inclusion Criteria

Inclusion criteria for the proposed study are:

- BMI \geq 50 kg/m²
- Determined to be a good candidate for surgery based on medical and psychological exam.
- Willing to participate in a 3-6 month medically supervised weight loss plan prior to surgery.
- Planning to remain in the reasonable vicinity of the Wake Forest Baptist Health Weight Management Center for the duration of the study.

Exclusion Criteria

- History of prior weight loss surgery (removal/conversion from band to sleeve will not be excluded)

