- Pregnant (women of childbearing potential will complete a pregnancy test (blood draw) to make sure they are not pregnant at the time that they initiate the medication). Ongoing monitoring of pregnancy status is the responsibility of the patient and they are instructed as such in the consent form.
- Ongoing use of weight loss medication
- Contraindications to use of Qsymia, including pregnancy, history of glaucoma, unstable cardiac disease (unstable angina, recent heart attack or stroke (in the past 6 months), uncontrolled arrhythmia), hyperthyroidism, taking MAOIs (monoamine oxidase inhibitors) or allergy to either topiramate or sympathomimetic amines like phentermine.

Patients may be removed from the study at any point if they are unable to tolerate the study medication or are less than 50% compliant with the study medication (take less than 50% of the recommended dose). If a patient is removed from the study due to medication intolerance or non-compliance, the study physician will meet with them and instruct them on how to stop the medication.

Primary endpoint

The primary endpoint for this study is the proportion of patients that meet the criteria to move forward with the second surgical procedure (Roux en Y Gastric Bypass). The criteria include all of the following at any point in the 24 month post-surgical follow up period:

1. Weight plateau (defined as weight gain or < 3 lbs weight loss) for at least 3 months
2. Remains above a BMI of 39.9 kg/m²
3. Continues to have obesity associated co-morbidities (Co-morbidities include hypertension, type 2 diabetes mellitus or pre-diabetes, hyperlipidemia, metabolic syndrome, obstructive sleep apnea, osteoarthritis, non-alcoholic steatohepatitis (NASH), gastroesophageal reflux disease (GERD)).

We hypothesize that the study group treated with Qsymia plus surgery will have a lower rate of occurrence of the primary endpoint at 24 months post-surgery compared to the group with surgery only.

Secondary endpoints

The secondary endpoints for this study are percent weight loss both before and after surgery and changes in percent body fat and resting metabolic rate.

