Increases in heart rate will be monitored. If > 100 beats per minute on 2 consecutive visits, participant will be withdrawn from medication and considered as endpoint reached. Metabolic acidosis will be monitored with basic metabolic panel at each follow up visit. The study clinic questionnaire will be used to monitor problems with the study drug, current dietary plan, vitals and mood changes. Any reports of abnormality on this form will be investigated further by the study physician and further action will be taken if necessary.

Depression and Suicidal Ideation

Change in mood will be assessed at each clinic visit via standard self-report questionnaire (See Clinic Questionnaire). Endorsement by participants of increased depressive symptoms will be reviewed and screened by the treatment provider at the time of the participant's appointment. Should the participant report changes in suicidal ideation, planning, or intent, the participant will be referred to the onsite Clinical Psychologist or referred to the local Emergency room for additional assessment and treatment recommendations. Participants who report significant distress associated with recent onset of mood symptoms will be provided with a list of referrals for local providers who offer counseling and psychopharmacological services. This protocol for assessment and treatment of mood symptoms is above and beyond recommended standard of care for monitoring depression and suicidal thoughts in patients taking Qsymia (topiramate) and other antiepileptic drugs (AEDs).

As a part of standard of care and consistent with guidelines published by the American Society of Metabolic Medicine, all participants will participate in psychosocial evaluation, prior to undergoing weight loss surgery. During this evaluation current/past mood symptoms and suicidal ideation/planning/intent will be assessed via self-report mood measures, a personality inventory, and via clinical interview. Participants will not be cleared to proceed with surgery if they meet criteria for a suicide attempt within the past 12 months or have active suicidal ideation, planning, or intent. Participants who are positive for these criteria will be referred for treatment; they will be reevaluated for bariatric surgery candidacy upon resolution of symptoms.

Safety Monitoring

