At each physician visit (monthly during phase one and at months 1, 3, 6, 9, 12, 15, 18, and 24 during phase 2) the participant will complete an adverse events questionnaire in addition to the signs and symptoms clinic questionnaire. All adverse events will be reviewed by the study coordinator to clarify any details or questions about the reported event. The PI will then review each adverse event and determine the likelihood that the event was related to the study and whether or not it was an expected event. Study clinicians will also review the medical record at clinic visits to determine if any event or medical care occurring in the interim was related to safety and/or side effects. Any event requiring immediate reporting will be reported as such. All adverse event data will be recorded in RedCAP and tabulated every 6 months for cumulative review. The PI will be responsible for reporting cumulative frequencies of adverse events for those on study drug. Additionally, any derangements in blood

chemistries that are being monitored as part of this study will be cataloged, and frequencies will be reported for all study participants every 6 months.

Participants will be asked to bring in their pill bottles to count any remaining pills at each visit. Missed doses of medication will be noted and any excess medication will be discarded at the refill visits in the hazardous waste containers per clinic protocol. Participants will be provided with only the medication required to provide daily doses until the next scheduled clinic visit.

Some patients enrolled in the study may have diabetes and be on hypoglycemic medications or insulin prior to surgery. As part of usual care, individuals with diabetes are instructed to reduce all diabetes medication by 50% before leaving the hospital after weight loss surgery and are instructed to follow-up with their primary care provider 2 weeks after surgery in order to monitor or modify medications for diabetes and other comorbid conditions such as blood pressure. In addition, discharge documents are sent to each patient's primary care provider either through Wake One or in paper form. Prior to surgery, patients are expected to develop a relationship with a primary care provider.

Statistical analysis

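### The only pregnancy test stated is at first initiation of Qsymia; none is stated before the post-operative restart at least 3 months later, or at later dispensing

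*Combined protocol and SAP*

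**What the plan says.** Under Exclusion Criteria, pregnancy appears twice: as an exclusion in its own right and among the contraindications to Qsymia. Women of childbearing potential are to "complete a pregnancy test (blood draw) to make sure they are not pregnant at the time that they initiate the medication". The next sentence states who is responsible after that: "Ongoing monitoring of pregnancy status is the responsibility of the patient and they are instructed as such in the consent form".

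The Treatment Group section sets the dosing sequence. Before surgery, "Patients will receive medical weight loss therapy for a minimum of 3 months prior to proceeding to the laparoscopic sleeve gastrectomy". The drug is stopped in the week before the operation. Afterwards, "Qsymia will be resumed in the second post-operative week at the initial titration dose".

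On supply, Safety Monitoring says: "Participants will be provided with only the medication required to provide daily doses until the next scheduled clinic visit". On laboratory follow-up, the section on monitoring side effects says: "Metabolic acidosis will be monitored with basic metabolic panel at each follow up visit".

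**The concern.** The plan does not rely on the patient's own report at first dose; it requires a blood test. The same contraindication applies when the drug is restarted after surgery and each time more is supplied, yet no site check is stated at those points and no reason is given for the difference.

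What is at stake is avoidable exposure. A woman who conceives between the first test and the restart, or during post-operative treatment, could be given a drug that the protocol itself says is contraindicated. As written, the safeguard is that she notices and tells the site.

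**Working it through.** The plan gives no figure on this point to reproduce. The check is a reading of every place where a test could be stated, followed by date arithmetic.

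**1. Where a test could appear**

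- Exclusion Criteria: one blood test, tied to initiation.
- Treatment Group, restart step: none stated. The plan describes this step as resuming the drug, so the initiation test does not naturally cover it.
- Schedule table: no pregnancy row. Research blood is drawn at baseline and months 3, 6, 12, 18 and 24, and is stored for later analysis.
- Monitoring of side effects: mood, heart rate, a basic metabolic panel, and a questionnaire on drug problems, diet, vitals and mood. Pregnancy is not mentioned.
- Safety Monitoring: adverse-event questionnaire, record review and pill counts. Pregnancy is not mentioned.

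**2. Age of the only stated test at restart**

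Inputs: pre-operative therapy of at least 3 months (Treatment Group), and restart in the second post-operative week, taken as days 8 to 14. I assume that the test and first dose fall at the start of medical therapy, and use 30.44 days per month.

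- Age = pre-operative duration + days from surgery to restart.
- Minimum duration: 3 × 30.44 = 91.3 days; 91.3 + 8 = 99.3 and 91.3 + 14 = 105.3, so about 99 to 105 days.
- With a 6-month phase (Inclusion Criteria mention a 3 to 6 month plan): 6 × 30.44 + 14 = 196.6, about 197 days. This is not a cap, because the Treatment Group section sets only a minimum.

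**3. Length of the pause**

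About 1 week before surgery plus 1 to 2 weeks after it gives 2 to 3 weeks off drug. The restart is thus a distinct step at which a test could be required.

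**4. Visit spacing after surgery**

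- Treatment Group: months 1, 3, 6, 9, 12, 18, 24 (7 visits); gaps 2, 3, 3, 3, 6, 6 months.
- Safety Monitoring adds month 15 (8 visits); gaps 2, 3, 3, 3, 3, 3, 6 months.

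On either list the longest gap is 6 months.

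**5. Blood available for a test**

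The first scheduled post-operative visit, at month 1, falls after the restart in week 2, so a restart test needs its own sample. From month 1 on, the metabolic panel provides blood at each follow-up visit. The research draws do not cover months 1, 9 or 15, so an added assay at those visits depends on the panel.

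**The case against.** The strongest reply is that this is a declared choice and not an oversight: the protocol assigns ongoing monitoring to the patient and says she is so instructed. That is right, and the consent form may cover contraception, home testing and stopping the drug. Those pages are not available, so the quality of the instruction cannot be judged. What stands against the reply is that a site test is thought necessary at the first dose and none is stated at the second start.

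A reader might infer that no pregnancy test is done around surgery. The documents do not support that. They do not itemise the pre-operative work-up, and a routine hospital test is possible. They show only that the protocol does not require one.

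A reader might also infer that women are handed 6 months of drug at a time. Physician visits can be 6 months apart, but Safety Monitoring also mentions refill visits, and the Statistical analysis section mentions a weekly clinic questionnaire. Whether refills shorten the supply interval is unclear.

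Nor does one test cover at least 3 + 24 = 27 months for everyone. That is planned exposure, less the pause, for a woman who stays on drug to month 24. Some will leave for intolerance, poor compliance or a withdrawal rule, and those who reach the endpoint may move to a second operation.

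Finally, a reader might argue that pregnancy weight gain could be scored as a plateau and distort the primary endpoint. This does not carry the point. The completers rule may exclude a treated woman who stops Qsymia, although its wording is unclear. No pregnancy rate is given. One extra treated failure at roughly the planned rates (7/25 v 14/20 in place of 6/25 v 14/20) moves the uncorrected chi-squared p-value only from 0.002 to 0.005.

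The monthly pre-operative visits, adverse-event questionnaires and record review are real but partial backstops.

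**Conclusion.** The point holds as a safety improvement. Following the plan as written, Qsymia can be restarted on the strength of a pregnancy test at least 3 months plus about 1 week old, and then supplied for up to 24 months after surgery to those who stay on drug, with no further test stated.

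This rests on reading initiation as the first dose only, and on the documents as provided. The number of women affected cannot be estimated: the documents give neither a pregnancy rate nor the expected number of women of childbearing potential. The case for change rests on an avoidable exposure and a cheap remedy, not on an expected count. It does not bear on the trial's primary comparison.

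**What to change.** Add to the Treatment Group and Safety Monitoring sections a rule to this effect: *women of childbearing potential must have a documented negative pregnancy test before Qsymia is restarted after surgery, and at each follow-up visit before further drug is supplied.* The follow-up test can be an assay added to the metabolic panel blood. The study clinicians should confirm the exact schedule, including whether the 6-month gaps need a test in between and whether the monthly pre-operative visits should include one. Patients who decline surgery but continue Qsymia have no restart, so only the follow-up testing would reach them; the schedule should say so.

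Cost: one separate test per woman at restart, plus one assay at each of 7 or 8 follow-up visits, or 8 to 9 tests per woman. If every treated patient were a woman of childbearing potential, the total would be between 20 × 8 = 160 and 25 × 9 = 225. The 20 and 25 are the two treated-group sizes given in the Statistical analysis and sample size sections. This is an upper bound for patients who have surgery under the minimum schedule; extra tests in the gaps or before surgery would add to it. At months 1, 9 and 15 the table lists no research draw, so the plan should make clear that the metabolic panel is taken at those visits.

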Qsymia Study

Principal Investigator: [name]

Investigators: [name]; [name], NP

Study Manager: [name], MS

NCT02301416

Scientific Basis/Rationale

While there is obvious focus on the obesity epidemic that affects approximately one-third of the U.S. population, one subgroup within the epidemic remains on the fringe of scientific study and effective treatment options. The super obese patient, in this instance defined as those with a BMI ≥ 50 kg/m², presents a difficult treatment challenge in managing this level of obesity. While bariatric surgery, including Roux-en-Y gastric bypass and biliopancreatic diversion with duodenal switch, have been shown to be effective in severe obesity (BMI ≥ 40 kg/m²), the risks involved with surgical intervention in the super obese patient are high. Perioperative morbidity is significantly higher, and mortality is as high as 5.2% at 1 year in some series (Nguyen et al, 2012). To address this issue, surgeons are offering patients a two-stage weight loss process that involves an initial laparoscopic sleeve gastrectomy, followed by the laparoscopic Roux-en-Y gastric bypass after initial weight loss. Some case series have reported improved morbidity and perioperative mortality similar to patients that are in lower BMI categories. A subset of patients using this approach will however not require the second surgery due to success with the first procedure. Alexandrou et al estimated that approximately 30% of patients lost sufficient weight to not require the second procedure in their experience (Alexandrou et al., 2012). Treatment plans that limit the need for the second procedure by promoting effective pre-operative and post-operative weight reduction as an adjunct to the surgical intervention would be valuable. These types of treatment plans would be valuable because they would decrease risk for the patient by eliminating the need for a second surgical procedure and there would be a reduction in cost for the patient and insurer/health system.

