This is an independent case-control study. Analyses will include completers only. Completers are defined as individuals who enter treatment and continue it (Qsymia and/or gastric sleeve) for at least 24 months without reversal or discontinuation. Participants will be recruited until the sample size of 20 cases is obtained. If a participant consents but does not have surgery, this person will not be counted as a case and thus, recruitment will continue.

Data will be entered into and stored in a REDCap database with access given only to individuals who are part of the study team. Study data uploaded will include information from the weekly clinic questionnaire, adverse events, as well as study outcomes (weight at clinic visits), demographic information, etc.

[figure not shown]
Most of the statistical analyses will be conducted using SPSS or SAS. Prior to testing the specific aims, descriptive statistics will be used to characterize the sample. Next, the groups will be compared using the chi-square statistic and T-test statistic to determine whether differences existed between the groups on key variables that may have an effect on outcomes. The case-control matching procedure should insure balance between the treatment groups on sex, age, BMI and ethnicity, but additional analyses will be used to examine the comparability between groups on baseline body composition, waist circumference, and resting metabolic rate.

The primary endpoint for this study is the proportion of patients that meet the criteria to move forward with the second surgical procedure (Roux en Y Gastric Bypass) at any point during follow up. The proportion of the Qsymia treated group that achieves the primary endpoint will be compared to the surgery only group after 24 months of follow up. Unadjusted and adjusted models will be developed to test for differences in the rate of the primary endpoint occurrence by treatment group.

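### The primary endpoint does not say how to score a second-stage operation performed before the three criteria are documented, a gap that falls mainly on the historical controls

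*Combined protocol and SAP*

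**What the plan says.** The Primary endpoint section of the combined protocol and SAP states: "The primary endpoint for this study is the proportion of patients that meet the criteria to move forward with the second surgical procedure". It continues: "The criteria include all of the following at any point in the 24 month post-surgical follow up period". The three conditions are a plateau, a BMI still above 39.9 kg/m² and continuing obesity-related co-morbidity. The plateau is worded as "Weight plateau (defined as weight gain or < 3 lbs weight loss) for at least 3 months". Statistical analysis repeats the criteria-based definition.

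In Treatment Plan, Treatment Group, the order is criteria first and operation second. Of patients who meet the criteria it says "These patients will be evaluated for the possibility of moving forward to the next operative stage"; everyone else stays on medication, diet and exercise.

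The Control Group section describes matched patients of the same centre, operated on before the study began and reviewed retrospectively. It gives no rule for ascertaining their events or for handling a bypass already done.

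Statistical analysis adds: "Analyses will include completers only". A completer continues Qsymia and/or the sleeve for at least 24 months with no reversal or discontinuation. Whether conversion of a sleeve to a bypass is a discontinuation is not stated.

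Monitoring of Side Effects to study medication adds two further routes to the endpoint (suicidal ideation, and raised heart rate on two consecutive visits). A performed second operation is not among them.

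**The concern.** The trial asks whether Qsymia reduces the need for a second operation, yet the operation itself does not enter the outcome. In the Qsymia group this should matter little, because the event is meant to come before the bypass. The controls were not bound by that order. A control who went to bypass before three months of plateau were on record had not met the first condition by then, and weight loss after the bypass makes a later plateau less likely.

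The plan leaves two ways to treat that patient: keep as event-free, or drop as a non-completer. If the patient would otherwise have been a failure, both lower the observed control failure rate, and they do so almost only in one group. Leaving the choice open also allows it to be made after the control charts have been read.

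The planning rate has a related problem. The control failure rate of 0.7 is the complement of the roughly 30% who, according to Scientific Basis/Rationale, lost enough weight not to require the second procedure. That describes need for the procedure and is not the three-condition rule.

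**Working it through.** **Inputs.** From Sample size justification/statistical power: control failure rate 0.70, experimental rate 0.25, alpha 0.05, uncorrected chi-squared, 25 experimental and 20 control subjects, stated power 0.840. From Statistical analysis: a target of 20 cases. Two-sided testing is assumed, since sidedness is not stated. The number m of control failures who had bypass before a documented plateau is not in the documents; 0 to 5 is an assumed range.

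**Formula.** Power = Φ{ [ |p1 − p2| − 1.96 √( p̄(1 − p̄)(1/n1 + 1/n2) ) ] / √( p1(1 − p1)/n1 + p2(1 − p2)/n2 ) }, where group 1 is control and p̄ is the pooled proportion.

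**The plan's own figure.**
- 20 v 20: p̄ = 0.475, so the numerator is 0.45 − 1.96 × 0.1579 = 0.1405. The denominator is 0.1410, the ratio 0.997 and the power 0.8405.
- 25 v 20 as printed: p̄ = 0.45, so the numerator is 0.45 − 1.96 × 0.1492 = 0.1575. The denominator is 0.1342, the ratio 1.174 and the power 0.880.

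The stated 0.840 therefore matches 20 v 20, not the 25 v 20 beside it. Both sizes are carried below.

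**Effect of m early-bypass controls.** Expected control failures are 0.70 × 20 = 14.
- Scored event-free: control rate (14 − m)/20, with 20 controls.
- Excluded without replacement: control rate (14 − m)/(20 − m), with 20 − m controls.

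| m | Rate, event-free | Power 20 v 20 | Power 25 v 20 | Rate, excluded | Power, 20 cases | Power, 25 cases |
|---|---|---|---|---|---|---|
| 0 | 0.70 | 0.841 | 0.880 | 0.700 | 0.841 | 0.880 |
| 1 | 0.65 | 0.738 | 0.786 | 0.684 | 0.800 | 0.843 |
| 2 | 0.60 | 0.617 | 0.670 | 0.667 | 0.751 | 0.797 |
| 3 | 0.55 | 0.490 | 0.540 | 0.647 | 0.694 | 0.742 |
| 4 | 0.50 | 0.368 | 0.409 | 0.625 | 0.629 | 0.676 |
| 5 | 0.45 | 0.258 | 0.289 | 0.600 | 0.555 | 0.601 |

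Worked case, m = 2, 20 cases:
- Event-free: (0.35 − 1.96 × 0.1563)/0.1462 = 0.298, power 0.617.
- Excluded: (0.4167 − 1.96 × 0.1615)/0.1474 = 0.679, power 0.751.

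The expected difference shrinks from 0.45 to 0.60 − 0.25 = 0.35, or to 0.667 − 0.25 = 0.417. If the two excluded controls were replaced to restore 20, power would be 0.774 (20 cases) or 0.821 (25 cases). Exact enumeration for m = 2 gives 0.610 and 0.731 with 20 cases and 0.670 and 0.807 with 25, so the pattern does not depend on the normal approximation.

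**The case against.** A reader might infer that an early-bypass control is definitely scored as a success. The documents do not go that far. A sleeve converted to a bypass can be read as not continued for 24 months, in which case the patient leaves the analysis. Exclusion costs less power than event-free scoring, as the table shows, but it still lowers the control rate.

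A reader might also infer that such controls exist, because the rationale describes the second stage as "followed by the laparoscopic Roux-en-Y gastric bypass after initial weight loss". That phrase describes what surgeons offer in general. It does not describe this centre's practice, and it is compatible with a plateau having occurred. No document shows that any control had an early bypass, so every value of m above zero is an assumption.

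It is also tempting to say that a control operated on early plainly needed the second operation. The documents do not support that either. A Qsymia patient still losing weight is not an event under the plan, and an operated control in the same state might later have fallen below the BMI threshold.

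Finally, an endpoint based on meeting criteria keeps uptake and timing decisions out of the outcome and may well be deliberate. Counting every performed bypass could bias the other way: each control operated on who would never have met the criteria adds 1/20, or 5 points, to the control rate. This argument stands, and it is why the remedy needs two analyses. It does not remove the gap, because the present text leaves the scoring of such a patient unsettled.

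**Conclusion.** The plan is incomplete on a point that can produce a wrong result. The event is defined only by the three criteria, and neither the endpoint nor the completer rule says what happens to a patient whose second operation comes first. Since only the Qsymia group is held to the order of criteria then operation, the gap falls mainly on the controls. Under either available reading it lowers their observed failure rate, provided the affected patients would otherwise have been failures.

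Event-free scoring costs 5 points of control rate per patient. With two affected controls, power is 0.62 or 0.75 instead of 0.84 at 20 v 20, and 0.67 or 0.80 instead of 0.88 at 25 v 20. These figures rest on the planning rates, on two-sided testing and on an assumed m. Because the frequency is unknown and the study is a pilot, the point should be corrected but does not by itself invalidate the design.

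**What to change.** Amend Primary endpoint and Statistical analysis as follows; only scoring changes, not patient care.

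1. State that conversion to a second-stage operation is not a discontinuation under the completer rule.
2. For every patient in both groups, abstract the date of any second weight-loss operation within 24 months of the sleeve, the reason for it, and which of the three criteria were met at that time.
3. Do not use weights recorded after that operation to score a patient event-free.
4. Define the event in both groups as all three criteria met or a second-stage weight-loss operation performed, whichever comes first.
5. Report the two components by group. Prespecify a criteria-only sensitivity analysis that judges each patient on data up to any second operation, and list patients operated on without having met the criteria.
6. State that a conclusion will be drawn only if both versions agree, because control operations may have been done for other reasons or under looser timing, so the composite can favour Qsymia.

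The cost is a few sentences of text, a small addition to the chart-review form and one extra analysis. The wording should be settled before control charts are abstracted.
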